#### 6.10.6 Expectedness

An unexpected AE is any AE, the nature and severity of which is not consistent with the applicable product information (e.g., Investigator’s Brochure for an investigational product or product label/summary of product characteristics for an approved product).

#### 6.10.7 Clinical Significance

The Investigator or medically qualified sub-investigator, trained on this study protocol, listed on the 1572 form or equivalent document and on the delegation of authority form is responsible for determining clinical significance of abnormal assessment results (e.g., laboratory or ECG results) for the subject.

### 6.10.8 Clinical Laboratory Adverse Events

Changes in laboratory values or vital signs, or other safety parameters (e.g., ECG, neurological and clinical symptom assessments) as noted in the protocol are a subset of AEs and are reportable only if considered to be clinically significant by the investigator or medically qualified sub-investigator except that:

- Baseline assessments are differentiated from AE/symptoms that are incurred post informed consent. These baseline lab assessments, if determined to be clinically significant abnormal values, reflect the status of the subject prior to study participation. These clinically significant pre-dose abnormal assessments without clinical symptoms will not be reported as AEs.

### 6.10.9 Serious Adverse Events

#### 6.10.9.1 Definition

A SAE is defined as any AE occurring at any dose that results in any of the following outcomes:

- death,
- life-threatening AE,
- hospitalization or prolongation of existing hospitalization,
- a persistent or significant incapacity or substantial disruption of the ability to conduct normal life functions, or
- a congenital anomaly or birth defect.

“Important medical events may be considered an SAE when, based upon appropriate medical judgment, they may jeopardize the subject and may require medical or surgical intervention to prevent one of the outcomes listed in this definition.”

#### 6.10.9.2 Reporting Serious Adverse Events

All SAEs must be reported to the Sponsor by the Investigator or designee by email or fax within 24 hours of discovery, using the form provided by the Sponsor. The SAE report should also be emailed to the Sponsor Medical Monitor.

In the event of an SAE, the Investigator or designee will notify Medical Monitor and the Indivior Pharmacovigilance:

Medical Monitor:

24-hour emergency number: [contact]

Email: [[contact]](mailto:[contact])

Indivior Pharmacovigilance:

Email: [[contact]](mailto:[contact])

[contact]  
Indivior Inc.  
[name]  
[name]

The Investigator or designee must inform the IRB immediately regarding any AE (does not have to be causally related) that is both serious and unexpected; or that represents a series of AEs that on analysis is unanticipated, or occurs at an unanticipated frequency, or otherwise represents an unanticipated safety risk to the study subject. The IRB may subsequently choose to modify the informed consent or request changes to the protocol or Investigator's Brochure. A PK sample will be taken as soon as possible after any SAE is reported. If possible, an additional sample should be collected when the SAE has been resolved.

#### 6.10.10 Treatment-Emergent Adverse Events

A TEAE is an AE that either commenced following initiation of study drug or was present prior to the initiation of study drug, but increased in frequency or severity following initiation of treatment, regardless of causality.

#### 6.10.11 Procedures and Follow-Up of Subjects with Ongoing SAEs or Experiencing SAEs after Completion of or Withdrawal from the Study

Subjects with SAEs ongoing at the end of the study or after ET will be followed by the Investigator until stabilization or resolution. If a subject experiences the onset of an SAE within a period of 30 days following study completion or withdrawal and, in the opinion of the Investigator or medically qualified sub-investigator, it is associated with the study, it will be followed up and reported as described for other SAEs.

#### 6.10.12 Pregnancy

If a female subject believes she is pregnant (e.g., missed period, self-administered pregnancy test) the subject will be instructed to return to the clinical unit within 48 hours to undergo a serum pregnancy test. If a pregnancy in a subject is confirmed at any time during the study through a serum pregnancy performed by the study laboratory, the subject will be discontinued from the study and will undergo all final study visit procedures (with the exception of a urine pregnancy test). If the partner of a study subject becomes pregnant, the pregnancy will be reported to the clinical unit within 48 hours of the subject's knowledge of the pregnancy. The Investigator will attempt to collect pregnancy information on any female partner of a randomized male study subject who becomes pregnant while participating in this study. After obtaining the necessary signed informed consent from the female partner directly, the Investigator will record pregnancy information on the appropriate form and submit it to Indivior or designated representative within 24 hours of learning of the partner's pregnancy.

All confirmed pregnancies that occur within this study will be followed until resolution (i.e., termination [voluntary or spontaneous] or birth).

Pregnancy ([study subject or the partner of a study subject] [without associated unexpected or adverse sequelae]) is not a reportable AE but must be reported to the Sponsor within 24 hours of the Investigator or study staff first being aware of the subject's condition.

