### 4.2 Inclusion Criteria

A. **De novo Subjects:** Subjects who have not participated in Study RB-US-13-0001 must meet the following criteria to be enrolled in this study:

1. Subjects seeking treatment for opioid use disorder who currently, and by medical history over the previous 3 months, meet the DSM-5 criteria for moderate or severe opioid use disorder.
2. Subjects who provide written informed consent to participate in this study.
3. Subjects who are an appropriate candidate for opioid partial-agonist treatment in the opinion of the Investigator or medically responsible physician.
4. Either male or female.
5. Age  $\geq 18$  to  $\leq 65$  years.
6. Have a body mass index (BMI) of  $\geq 18.0$  to  $\leq 35.0$  kg/m^2.
7. **Females:** Women of childbearing potential (defined as all women who are not surgically sterile or postmenopausal for at least 1 year prior to informed consent), must have a negative pregnancy test prior to enrollment and must agree to use a medically acceptable means of contraception from screening through at least 6 months after the last dose of investigational medicinal product (IMP).

**Males:** Subjects with female partners of child-bearing potential must agree to use medically acceptable contraception after signing the informed consent form (ICF) through at least 6 months after the last dose of IMP. Male subjects must also agree not to donate sperm during the study and for 6 months after receiving the last dose of IMP.

The following methods of contraception are considered to be medically acceptable: established use of oral, injected or implanted hormonal contraception; placement of an intrauterine device or intrauterine system; use of a double-barrier method of contraception (condom or occlusive cap with use of a spermicide) or male sterilization.

8. Subjects must agree not to take any buprenorphine products other than those administered during the current study throughout participation in the study.
9. Subjects must be willing to adhere to study procedures.

B. **Roll-Over Subjects:** Subjects who have successfully completed Study RB-US-13-0001 in its entirety must complete EOS/Day 169 assessments, which will serve as screening for this study. In addition, **only** the following criteria must be met to be enrolled in this study:

1. Provide written consent to participate in this study.
2. Be considered eligible in the medical judgment of the Investigator.

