3. **Females:** Women of childbearing potential (defined as all women who are not surgically sterile or postmenopausal for at least 1 year prior to informed consent) must have a negative pregnancy test prior to enrollment and must agree to use a medically acceptable means of contraception from screening through at least 6 months after the last dose of IMP.

**Males:** Subjects with female partners of child-bearing potential must agree to use medically acceptable contraception after signing the ICF through at least 6 months after the last dose of IMP. Male subjects must also agree not to donate sperm during the study and for 6 months after receiving the last dose of IMP.

The following methods of contraception are considered to be medically acceptable: established use of oral, injected or implanted hormonal contraception; placement of an intrauterine device or intrauterine system; use of a double-barrier method of contraception (condom or occlusive cap with use of a spermicide) or male sterilization.

4. Subjects must agree not to take any buprenorphine products other than those administered during the current study throughout participation in the study.

5. Subjects must be willing to adhere to study procedures.

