### 6.15.3 Additional Care of Study Subjects Following Completion of the Study

Each subject will be evaluated on his or her final study day. Subjects who experience SAEs at the EOS, or experience the onset of an SAE after the final visit, will be followed up as described in Section [6.10.11](#). No other additional care of study subjects will take place following completion of the study.

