9.6.4.5 Other Safety Variables

Urine pregnancy results will be listed.

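### Contraception is required for at least 6 months after the last dose, but pregnancy follow-up to outcome and partner data collection stop with the study, and the SAP text lists only urine tests

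*Protocol*

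**What the plan says.** **Contraception period.** Protocol section 4.2, criteria A7 (de novo) and B3 (roll-over), applies to women of childbearing potential "from screening through at least 6 months after the last dose of investigational medicinal product". Male subjects with partners of childbearing potential are bound for the same time; for roll-over men the text is "medically acceptable contraception after signing the ICF through at least 6 months after the last dose of IMP".

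**Pregnancy rules.** Protocol section 6.10.12 contains three rules with different scopes:
- Follow-up: "All confirmed pregnancies that occur within this study will be followed until resolution".
- Partner data: the investigator tries to collect information on the partner of a *randomized* male subject "who becomes pregnant while participating in this study".
- Reporting: a pregnancy in a subject or a partner, even if uncomplicated and so not an adverse event, "must be reported to the Sponsor within 24 hours of the Investigator or study staff first being aware". No end date is given.

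**Contact after the last injection.** Appendices 3 and 5 place the last urine pregnancy test at EOS. The later safety call covers adverse events and concomitant medications; pregnancy is not named. Subjects who enroll in INDV-6000-301 need no call (section 3.3). Apart from SAE follow-up, section 6.15.3 states: "No other additional care of study subjects will take place following completion of the study".

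**Analysis.** SAP section 9.6.4.5 has one sentence: "Urine pregnancy results will be listed". SAP Appendix 3 places the table and listing shells in a separate document, which was not available.

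**The concern.** The sponsor has judged that pregnancy should be avoided for at least 6 months after the last injection of a long-acting depot. A reader would expect the rules for following pregnancies to span the same period. They do not: follow-up to outcome and partner data collection are tied to the study, and study contact ends well before 6 months.

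The primary objective is long-term safety. If a pregnancy begins in the later part of the contraception period and the site hears of it, the protocol does not require anyone to find out how it ended. If the site does not hear of it, nothing in the section or the schedules asks the subject at the last visit to make it known. The planned outputs, as far as the SAP text shows, would not bring together the pregnancies that are known.

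**Working it through.** No sample-size or power figure is involved. The check is calendar arithmetic followed by a comparison of the three rules.

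**1. Reproduce the plan's own durations** (Protocol section 3.3: 7-day screening, 14-day run-in, 48 or 24 weeks of treatment, 4 weeks to the call).
- De novo: (7 + 14 + 48×7 + 28)/7 = 385/7 = 55 weeks, as stated.
- Roll-over: (7 + 14 + 24×7 + 28)/7 = 217/7 = 31 weeks, as stated.

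**2. Last injection to last test and last call** (Appendices 3 and 5, nominal days).

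| Cohort | Last injection | EOS (last urine test) | Call | Days to test | Days to call |
|---|---|---|---|---|---|
| Roll-over | Day 141 | Day 169 | Day 197 | 28 | 56 |
| De novo | Day 309 | Day 337 | Day 365 | 28 | 56 |

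**3. Share of the contraception period after the last contact.** Six months is taken as 183 days.
- 183 − 56 = 127 days; 127/183 = 69%.
- With 6 months as 180 days: 124/180 = 69%. As 184 days: 128/184 = 70%.
- With the −2/+4 day windows on both the injection and the call, the gap between them runs from 56 − 6 = 50 to 56 + 6 = 62 days. The share is then (183 − 50)/183 = 73% to (183 − 62)/183 = 66%.

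**4. Does the SAE rule fill the gap?** Section 6.10.11 covers SAEs that start within 30 days after completion or withdrawal and are judged associated with the study. Counting those 30 days from the call, the latest possible start, gives 56 + 30 = 86 days. Then 183 − 86 = 97 days, or 53%, remain. A congenital anomaly is an SAE (section 6.10.9.1), but for a pregnancy conceived after day 56 it would normally be found at or near birth, long after day 86.

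**5. The rules side by side, for a pregnancy conceived after the call but within 6 months and made known to the site.**
- Reporting within 24 hours: applies on its wording, since the duty runs from awareness.
- Follow-up to outcome: not required, because the pregnancy did not occur within the study.
- Partner data: not required, because the subject is no longer participating.
- Prompt to the subject: section 6.10.12 and the EOS/ET columns contain no instruction to report it. The consent form was not available.

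**6. The word *randomized*.** SAP section 3.2 states that the study involves no randomization, so taken literally the partner-data sentence applies to no subject.

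**7. SAP output.** A listing of subjects' urine tests can show a positive test. It cannot show a serum confirmation, a partner's pregnancy or an outcome.

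**The case against.** The strongest reply is that the protocol already catches most of what matters. The 24-hour duty covers subjects and partners and has no end date. The sentence asking a male subject to tell the unit within 48 hours of learning of a partner's pregnancy has no end date either. Partner data go to the sponsor on a dedicated form, so the absence of a SAP listing does not mean the information is lost. Pregnancy with adverse consequences is not exempt from adverse-event status, all SAEs on the case report form are listed (SAP 9.6.1.2), and discontinuation reasons are listed (SAP 9.1). Section 6.15.3 is about care, not reporting.

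Most of this stands, and it rules out several stronger readings that a reader might infer:
- *Pregnancies after the study are not reportable.* The restricting words attach to follow-up and partner data, not to the reporting duty.
- *The SAP shows no pregnancies.* It lists urine results, and the shells cannot be checked.
- *Subjects who receive no call lose even more of the period.* The only subjects exempted are those entering INDV-6000-301, another RBP-6000 study whose pregnancy rules are not in these documents.
- *The 6 months is a stated fetal-risk period, or a half-life calculation measures the risk.* Section 4.2 gives a contraception requirement without that rationale. The longest half-life in section 1.4.2 comes from single doses of 200 mg, a dose not used here; section 1.4.3 describes a more complex absorption profile than simple decline; and nothing links remaining levels to fetal outcome.

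The reply does not supply a duty to follow a later pregnancy to its outcome, or an instruction to the subject at the last visit.

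**Conclusion.** The point holds in limited form and is minor. The contraception period and the pregnancy follow-up period do not match. For subjects who complete on schedule and do not enter INDV-6000-301, about 127 of 183 days (69%; 66% to 73% across visit windows) fall after the last planned contact. A site that follows section 6.10.12 exactly would report a later pregnancy it hears of, but need not follow it to outcome or collect partner data. Beyond the urine-test listing, the SAP text plans no output of confirmed pregnancies, partner pregnancies or outcomes.

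This rests on nominal visit days, on 6 months taken as 183 days, and on the text of the two documents without the shells or the consent form. For subjects who leave early, the time from last dose to last contact depends on when they leave and was not calculated. The percentage describes calendar time, not the number of pregnancies expected, for which the documents give no basis.

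**What to change.** **Protocol 6.10.12.** State that any pregnancy in a subject, or in a male subject's partner, conceived up to 6 months after the last dose and known to the site is reported within 24 hours and followed to outcome, with the partner's own consent as the section already requires. Delete *randomized*. For subjects entering INDV-6000-301, refer to that protocol.

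**EOS/ET visit.** Instruct subjects to tell the site of any such pregnancy.

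**SAP 9.6.4.5.** Add one listing of all known pregnancies: subject or partner, days since last dose, and outcome where known. Outcomes that arrive after database lock are handled through the safety database.

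**Cost.** Wording changes, one instruction and one listing. No visit or call is added and the contraception rule is unchanged. Reporting remains passive, so capture will be incomplete, and a few more reports must be handled.

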## 6.11 Clinical Outcome Assessments

Clinical outcome assessments will include the UDS for opioids and other drugs; self-reported use of illicit opioids, other drugs, and alcohol on the TLFB; COWS, SOWS, and Opioid Craving VAS.

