On Day 1 of the study (initiation of study drug injections), all subjects will receive a SC injection of 300 mg of buprenorphine in RBP-6000. Subsequent doses of RBP-6000 may be adjusted down to 100 mg and back up to 300 mg based on the medical judgment of the Investigator. After injection of RBP-6000, subjects will not be permitted to receive supplemental SUBOXONE sublingual film during the RBP-6000 treatment period. Subjects who require supplemental SUBOXONE sublingual film or other sublingual buprenorphine pharmacotherapy during the RBP-6000 treatment period will be withdrawn from the study and referred for appropriate treatment.

Subjects will return to the clinic for monthly injection visits (every 28 - 2/+ 4 days) for a total of up to 12 injections for *de novo* subjects or for a total of 6 injections for roll-over subjects. ECG recordings and vital signs will be collected pre and post each SC injection. All ECGs will be interpreted by a central monitoring facility. Subject-reported injection site pain Visual Analog

Scale scores (VAS) will be collected at various times up to 1 hour after each injection. Local injection site grading will be collected at various time points starting immediately after injection and will be evaluated for pain, tenderness, warmth, itching, erythema, inflammation or swelling, and bruising using a 4-point severity scale. At each visit after injections begin, the injection site will be assessed by site staff and will also be evaluated for evidence of attempts to remove the depot.

Subjects will need to return to the clinic weekly for the first 5 weeks and biweekly (i.e., every 2 weeks) until injection 6, and monthly for the rest of the study period for urine drug screens (UDS), Timeline Followback (TLFB) interviews, opioid craving VAS evaluation, COWS and subject reported outcomes (Subjective Opiate Withdrawal Scale [SOWS]). Subjects will continue to receive counseling (manual-guided behavioral therapy) during the study.

Safety assessments will be collected at each visit and will include the following: vital signs, electronic Columbia Suicide Severity Rating Scale (eC-SSRS) responses, ECGs, laboratory tests (hematology, chemistry, urinalysis, and pregnancy test), concomitant medications, and AEs.

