### 6.11.1 Timeline Followback Interview

The TLFB Interview will be administered according to the SOE in [Appendix 1](#), [Appendix 2](#), [Appendix 3](#), [Appendix 4](#), and [Appendix 5](#). The TLFB Interview is a method to assess recent drug use and will be administered electronically. The questionnaire should be administered by an interviewer. The interview instrument asks subjects to retrospectively estimate their drug use in the 30 days prior to screen at the screening visit and since the last visit at all subsequent visits. Only occurrence of use is captured (i.e., used or did not use) (Fals-Stewart 2000). The interview takes approximately 10-30 minutes to complete and is appropriate for males and females 14 years of age and older. Drugs to be assessed in this study include opioids, methadone, buprenorphine, cocaine, barbiturates, benzodiazepines, amphetamines/methamphetamine, phencyclidine, and ethanol ([Appendix 17](#)).

The timeline followback interview should be completed prior to SUBOXONE and RBP-6000 injection and at approximately the same time each day  $\pm$  2 hours.

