## 9.6 Secondary Analysis

### 9.6.1 Clinical Outcomes Assessments

COWS, SOWS and Opioid Craving VAS total scores will be summarized using descriptive statistics (mean, median, SD, minimum, maximum), including change from baseline. Subjects' self-reported illicit drug use from the TLFB will be summarized using descriptive statistics.

The cumulative distribution function (CDF) of the percentage of urine samples negative for opioids and that of the percentage of self-reports from the TLFB negative for illicit opioid use will be calculated. Other outcome efficacy measures will be estimated using descriptive statistics.

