### 5.2 Respiratory Depression

Buprenorphine, particularly when taken by the IV route, in combination with benzodiazepines or other CNS depressants (including alcohol), has been associated with significant respiratory depression and death. Many, but not all, post-marketing reports regarding coma and death associated with the concomitant use of buprenorphine and benzodiazepines involved misuse by self-injection. Deaths have also been reported in association with concomitant administration of buprenorphine with other depressants such as alcohol or other CNS depressant drugs. Patients should be warned of the potential danger of self-administration of benzodiazepines or other depressants while under treatment with SUBOXONE sublingual film [*see Drug Interactions (7.3)*].

**In the case of overdose, the primary management should be the re-establishment of adequate ventilation with mechanical assistance of respiration, if required. Naloxone may be of value for the management of buprenorphine overdose. Higher than normal doses and repeated administration may be necessary.**

SUBOXONE sublingual film should be used with caution in patients with compromised respiratory function (e.g., chronic obstructive pulmonary disease, cor pulmonale, decreased respiratory reserve, hypoxia, hypercapnia, or pre-existing respiratory depression).

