4.2 Secondary Variables

The following secondary variables will be evaluated to analyze clinical outcomes:

- COWS total score.
- SOWS total score.
- Opioid Craving VAS total score.
- Self-reported illicit drug use.
- Percentage of negative urine drug screen samples.

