use, as defined in [Section 5](#); for example, 10% on the x-axis represents the proportion of subjects who had at least 10% of their self-reported opioid drug use combined with UDS as abstinent.

Additionally, a table showing the percentage of subjects with negative results at each visit will be provided.

All missing results for opioids were considered nonnegative for opioids. Opioids non-negative indicates detection of buprenorphine (only self-reports), codeine, hydrocodone, hydromorphone, methadone, morphine, opiates, oxycodone, and oxymorphone in the urine drug screen and reporting of amphetamine/methadone, buprenorphine, methadone, and opioids use in the timeline followback.

The number and percentage of subjects abstinent between visits will be summarized by subject type for the Safety Analysis Set. Additionally, the time to first urine sample non-negative or TLFB self-report of non-negative for opioids will be analyzed in the Safety Analysis Set for subjects who are Abstinent on Day 1 using Kaplan-Meier analysis methods to determine the first quartile (25%) and median (days) along with their corresponding confidence intervals in each subject type and overall. Subjects who are abstinent throughout the trial will be censored on the date of their last negative urine sample of TLFB self-report for opioids.

The number and percentage of subjects who have a non-negative result in each substance tested in the UDS will be reported by subject type in the Safety Analysis Set. Additionally, the number and percentage of subjects at each visit who tested non-negative for non-opioid substances will be summarized by subject type in the Safety Analysis Set in a tables and in figures for amphetamine, barbiturates, benzodiazepine, cannabinoids, and phencyclidine.

Opioid TLFB and UDS results will be listed together. Additionally, all drugs identified in the TLFB interviews and detected in the UDS will be listed separately for the Safety Analysis Set.

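### The SAP sends the non-opioid TLFB items, alcohol included, to a listing only, although the protocol names them as clinical outcomes; ethanol has no on-treatment summary in this SAP

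*Protocol*

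**What the plan says.** Protocol 6.11 includes "self-reported use of illicit opioids, other drugs, and alcohol on the TLFB" in its list of clinical outcome assessments. Protocol 6.11.1 names the items: "Drugs to be assessed in this study include opioids, methadone, buprenorphine, cocaine, barbiturates, benzodiazepines, amphetamines/methamphetamine, phencyclidine, and ethanol". After screening, each interview asks about use "since the last visit at all subsequent visits". The form in Appendix 17 records use or no use by date.

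On analysis, Protocol 9.6.1 states that "self-reported illicit drug use from the TLFB will be summarized using descriptive statistics". It adds that other outcome measures will be estimated descriptively. SAP 4.2 keeps "Self-reported illicit drug use" as a secondary variable. Neither place restricts this to opioids.

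In SAP 9.5.1 every table and figure that uses the TLFB uses the combined opioid result from urine and self-report. For the remaining items the SAP says that "all drugs identified in the TLFB interviews and detected in the UDS will be listed separately for the Safety Analysis Set". The non-opioid tables and figures count subjects who tested non-negative, which is urine data. SAP 1.1 gives six changes from the protocol, and none concerns the TLFB.

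**The concern.** The protocol names an outcome and says it will be summarized. The SAP reduces it to a listing without saying so, although Protocol 9.1 requires deviations from its planned analyses to be included in the SAP. A listing of about 600 subjects over many visits does not tell a reader how common alcohol or benzodiazepine use was on treatment.

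The primary objective is long-term safety. The attached SUBOXONE label ties benzodiazepines and alcohol to respiratory depression. On alcohol it says: "Deaths have also been reported in association with concomitant administration of buprenorphine with other depressants such as alcohol or other CNS depressant drugs". SAP 9.6.1.9 and 9.6.1.10 plan adverse-event tables for respiratory and CNS depression. As written, the SAP gives no summary of on-treatment alcohol use, and none of self-reported benzodiazepine use, to read beside them.

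**Working it through.** No statistical figure is at issue. The check traces each TLFB item to the SAP outputs that use it.

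**Items.** The TLFB classification table in SAP 9.5.1 has 9 items. Four are classed as opioid and enter the composite: opioids, methadone, buprenorphine and amphetamine/methadone (the item mis-programmed on the tablet). That leaves 9 − 4 = 5 items, or 5/9 = 56%, with no TLFB table or figure. The extra COWS, SOWS and craving outputs also use the TLFB, but only to exclude illicit opioid users.

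| Non-opioid TLFB item | TLFB table or figure | Urine summary in SAP 9.5.1 |
|---|---|---|
| Barbiturates | none | per substance and by visit |
| Benzodiazepine | none | per substance and by visit |
| PCP | none | per substance and by visit |
| Cocaine | none | per substance, as benzoylecgonine; not named in the by-visit set |
| Ethanol | none | none |

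Ethanol is absent from the urine panel in both Protocol Table 2 and SAP 9.6.2.4. So 4 of the 5 substances have some on-treatment summary, and 5 − 4 = 1, ethanol, has none. Its only table in this SAP is the never/former/current category at baseline (SAP 9.3).

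**Time between samples.** After Injection 6 (Day 141), Protocol 3.1 has visits "monthly for the rest of the study period for urine drug screens (UDS), Timeline Followback (TLFB) interviews". De novo urine then falls on Days 169, 197, 225, 253, 281, 309 and 337. That is 7 samples covering 337 − 141 = 196 days, and 196/7 = 28 days apart. The TLFB at the same visits covers each 28-day interval in full. Roll-over subjects finish at Day 169, so the long stretch of 28-day spacing applies to de novo subjects.

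**Could ASI-Lite stand in?** It has an alcohol section with 30-day recall (Protocol 6.12.6, Appendix 23).

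- De novo: scheduled after baseline on Days 57, 141, 225, 309 and 337. The last two windows are 28 days apart and overlap by 2 days, so coverage is 5 × 30 − 2 = 148 of 337 − 1 = 336 days, or 44%.
- Roll-over: Days 57, 141 and 169, giving 3 × 30 − 2 = 88 of 169 − 1 = 168 days, or 52%.

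It covers part of the period, and SAP 4.3 sends it to a separate SAP.

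**The case against.** Several points on the other side stand.

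- **Alcohol is not an illicit drug.** The sentence in Protocol 9.6.1 on illicit drug use, and SAP 4.2, do not clearly reach it. For ethanol the commitment rests on Protocol 6.11 together with the general sentence in 9.6.1 on other outcome measures. For benzodiazepines, barbiturates, cocaine and PCP the illicit-use sentence applies directly.
- **The data are not lost.** All TLFB drugs are listed, four of the five substances have urine summaries, and benzodiazepines recorded as medications appear in the concomitant-medication table.
- **The TLFB is not the only view between samples.** ASI-Lite covers part of the time, and the schedules allow an extra urine screen if use is suspected. However, SAP 9.0 keeps unscheduled results out of the by-visit tables. The documents give no urine detection window, so how much of each interval urine misses is unknown.
- **Two documents cannot be seen.** The table shells (SAP Appendix 3) might contain a table that the SAP text does not describe. The health-economics SAP may summarize alcohol from ASI-Lite. A reader might infer that alcohol goes unsummarized across the whole study; the documents do not support a claim that wide.
- **TLFB ethanol is use or no use, without quantity.** One drink and intoxication score alike. ASI-Lite separates the two.

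A reader might also infer that the respiratory and CNS depression tables cannot be interpreted without co-use data. They are descriptive counts in an uncontrolled study, and the listings allow each case to be checked, so a co-use summary would help but is not a precondition. Nor can one conclude that co-use differs between de novo and roll-over subjects. Roll-over subjects have only three exclusion criteria here and case-by-case review of benzodiazepines started in the earlier study, but that study's entry criteria are not in the documents.

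None of this supplies the missing TLFB summary or its declaration.

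**Conclusion.** The point holds within limits. Five of the nine TLFB items, named in the protocol as clinical outcomes, have no on-treatment TLFB summary in this SAP, and the change is not declared. The count of five refers to self-report items. It should not be read as five substances going unreported, because only ethanol lacks any on-treatment summary in this SAP. For benzodiazepine, barbiturates, cocaine and PCP the loss is the self-reported use between urine samples, most relevant to de novo subjects after Day 141.

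The conclusion rests on the SAP text as written and assumes that the table shells add nothing it does not describe. It does not extend to the separate health-economics SAP. No estimate of a result is shown to be biased; the defect is that a planned outcome goes unsummarized.

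**What to change.** In SAP 9.5.1, add one table of TLFB ethanol, benzodiazepine, barbiturates, cocaine and PCP by subject type (de novo, roll-over, total) and visit, and at any time on treatment. For each item give:

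- n (%) of subjects reporting any use since the previous interview, among subjects interviewed at that visit;
- the percentage of TLFB days with use.

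Use observed data only; SAP 9.0 already says that missing non-opioid results are not imputed. The Day 1 interview takes place before the first injection, so show it as a pre-treatment column and leave it out of the on-treatment count. A footnote should say that the TLFB records use without quantity.

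If the sponsor decides against the table, SAP 1.1 should declare the omission and give the reason. Adding TLFB alcohol or benzodiazepine use to the respiratory and CNS depression outputs is optional; no protocol commitment requires it.

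The cost is a paragraph of SAP text and one extra table from data already collected, with no change for sites or subjects.
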